9.4. Background and Demographic Characteristics

Summaries for the demographics, baseline characteristics, medical history, prior medications, and protocol deviations will be presented for the mITT population by treatment groups. Concomitant medications will be presented for the Safety population by treatment groups. Individual listings will also be provided, including concomitant medical procedures for the Safety population.

9.5. Subject Disposition

The disposition of subjects will be summarized with numbers and percentages by treatment group for all enrolled subjects. Summaries will include the number and percentage of subjects in the following categories:

- Randomized, dosed (at least one dose of study treatment), permanently discontinued from IP, discontinued from the study, discontinued from IP and remained in study follow up, and completed study
- Primary reasons for discontinuation from the study

9.6. Efficacy Analysis

9.6.1. Efficacy Analysis of the Primary Endpoint

9.6.1.1. Percentage Change from Baseline in EASI Scores at Week 16

The primary efficacy endpoint of percentage change from baseline in EASI scores at Week 16 will be analyzed using an analysis of covariance (ANCOVA) model, based on the modified intent to treat (mITT) population, with treatment group indicators as the main effects adjusting for baseline EASI scores, and the stratification factors of vIGA-AD score (3 [moderate] or 4 [severe]) and region (Japan versus RoW) as covariates. For each of the active treatment arms, the adjusted mean percentage changes from baseline and corresponding differences versus placebo in EASI scores at Week 16 will be estimated (based on Least-Squares Means) along with 95% Wald confidence intervals (CIs) and p-values.

Missing EASI scores at Week 16 (eg, due to study dropout or other reasons for lack of assessment) will be handled using a multiple imputation (MI) approach (SAS Institute, 2015) under a missing at random (MAR) assumption. In the sequel we refer to this as the MI approach.

To adjust for multiplicity, a standard hierarchical approach will be utilized by conducting comparisons, each at the 2-sided 0.05 alpha-level (based on the aforementioned adjusted p-values), in the order of mg QW versus placebo, mg Q2W versus placebo, and mg Q2W versus placebo.

Sensitivity analyses will be conducted to support the primary analysis by utilizing an alternative missing data approach as well as by assessing the impact of rescue therapy. The first sensitivity analysis will replace the MI approach for missing EASI scores at Week 16 with imputation by LOCF (last observation carried forward). The second and third sensitivity analyses will evaluate the impact of rescue therapy by defining EASI scores after rescue therapy (prior to Week 16) initiation as missing. The second sensitivity analysis will apply the MI approach with the addition (further degree) of missingness due to rescue. The third sensitivity analysis will combine the first and second sensitivity analyses by replacing the MI approach in the second sensitivity analysis with LOCF.

9.6.1.2. Subgroup Analysis of Primary Endpoint

To assess whether the treatment effect is consistent across various groups, subgroup analyses will be performed for the primary endpoint at Week 16. Treatment differences and 2-sided 95% CIs will be provided for each subgroup listed below. Forest plots for the treatment differences by subgroup will also be provided.

- 1. Non-elderly adults [< 65 years] versus elderly adults [≥ 65 years])
- 2. vIGA-AD baseline score (4 versus 3)

- 3. Sex (female versus male)
- 4. Region (Japan versus Rest of world)
- 5. Race (white versus non-white)
- 6. Prior experience with systemic immunosuppressive drugs

If there are not enough subjects (eg, < 8% mITT population, based on observed cases) in each subgroup and treatment category, the corresponding subgroup analyses will not be performed; instead, summary statistics will be provided. Details will be described in the SAP

Additional planned subgroup analyses may be considered and further defined in the SAP.

9.6.2. Efficacy Analysis of Secondary Endpoints

9.6.2.1. Analysis Methods

For the first key secondary endpoint of proportion of subjects with both a vIGA-AD score of 0 (clear) or 1 (almost clear) and a reduction of 2 or more points in vIGA-AD score from Baseline at Week 16 will be analyzed based on the mITT population using a stratified Cochran-Mantel-CMH test at a two-sided 5% significance level. The randomization stratification levels are: (1) Japan region, (2) RoW region and vIGA-AD score 3, and (3) RoW region and vIGA-AD score 4. Estimates of the differences in proportions between each treatment group versus placebo, and associated 95% confidence intervals will be provided along with p-values. Missing endpoint values (eg, due to study dropout or other reasons for lack of assessment) will be imputed as non-responders. A sensitivity analysis will be conducted based on defining subjects who initiate rescue therapy (prior to Week 16) as missing and treated as non-responders.

The second key secondary endpoint of proportion of subjects with at least a 75% improvement from baseline in Eczema Area and Severity Index (EASI-75) at Week 16 will be analyzed in the same manner as above.

The hierarchical testing approach used for the primary endpoint will be utilized to adjust for multiplicity with respect to the 3 active doses for each of these key secondary endpoints. However, multiplicity adjustments are not implemented across the primary and 2 key secondary endpoints simultaneously.

The following endpoints will be analyzed in the same manner as the key secondary endpoints, excepting that p-values will not be provided:

- The secondary endpoint of proportion of subjects with Pruritus NRS change of ≥ 4 from Baseline at Week 16
- The secondary endpoint of proportion of subjects with a 90% improvement from Baseline in EASI (EASI-90) at Week 16

The following endpoints will be analyzed in the same manner as the primary endpoint, excepting that p-values will not be provided:

- The secondary endpoint of percentage change from baseline in Pruritus NRS at Week 16
- The secondary endpoint of percent change in SCORAD Scores from Baseline at Week 16

• The secondary endpoint of mean percent change in Body Surface Area (BSA) involved with AD from Baseline at Week 16

For the secondary endpoint of time to achieve at least 4 points of improvement in the severity of pruritus NRS scale in the first 16 weeks of treatment, the distribution of times to the first event of 4-point improvement will be compared based on Kaplan-Meier (K-M) and log-rank approaches. Comparisons versus placebo, for each dose group separately, will be based on a stratified log-rank test with associated p-value provided. The stratification levels are: (1) Japan region, (2) RoW region and IGA score 3, and (3) RoW region and vIGA-AD score 4. The K-M estimates for the cumulative proportions of subjects achieving a 4-point improvement, by specific timepoints, will be provided by dose group as well as differences with placebo and associated 95% confidence intervals. These will be reported at various timepoints (eg, Day 1 to 28, followed by weekly assessments). Censoring rules will be described in the SAP.

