7.2.6. Criteria for Discontinuation of Dosing

Dosing will be required to be permanently discontinued (treatment discontinuation) for a subject if the subject experiences any of the events listed below following initiation of IP.

• SAE which is suspected of being related to IP, and study treatment continuation could present an unreasonable risk to the subject as determined by the Investigator, or Sponsor.

- Experiences a severe or serious (per Investigator assessment) opportunistic infection (suggestive of subject being immunocompromised)
- Receives a malignancy diagnosis, excluding carcinoma in situ of the cervix or squamous or basal cell carcinoma of the skin if it can be successfully treated by local resection
- Experiences an anaphylactic reaction or other severe systemic reaction (eg, hypersensitivity, allergic, or autoimmune) suspected of being related to IP by the Investigator or the Sponsor

- Experiences 2 separate occurrences of severe injection site reactions (ISR) that last longer than 24 hours.
 - A severe ISR is defined as an ISR that manifests with symptoms causing severe discomfort/pain; symptoms requiring medical/surgical attention/intervention; interference with activities of daily life (ADLs) including inability to perform daily social and functional activities (eg, absenteeism and/or bed rest); and/or when drug therapy is required
- Becomes pregnant
- Uses prohibited systemic immunosuppressive or immunomodulating drugs
- Uses systemic rescue therapy
- Misses 3 or more consecutive doses

These subjects will be encouraged to remain in the study and complete all required study assessments (which the exception of dosing with IP) remaining in the treatment period and follow up period of the study. In order to prevent missing data, the site staff will ensure attempts are made to reach subjects by phone or email that do not maintain contact with the Investigator. Any subject discontinuing the study prematurely will be asked to complete the ET Visit and the Initial and the Final Follow-up Visits.

Additional events that are considered sufficient reasons for discontinuing a subject from the IP are summarized in Section 11.1.

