8. CONCOMITANT MEDICATIONS AND PROCEDURES

All treatments (including prescription and over the counter [OTC] medications, herbal and dietary supplements, dietary modifications, and procedures) used by subjects within the 4 weeks (28 days) prior to the first Screening Visit or at any time during the study are regarded as prior or concomitant treatments and must be documented on the appropriate section of the eCRF. In addition, a history of previous treatments for AD will be documented.

All concomitant treatments, including blood and blood products, used from 28 days prior to the first Screening Visit until the Final Safety Follow-up Visit, or Final Study Visit must be reported on the eCRF.

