8.4. Rescue Medication

In the event a subject develops intolerable AD symptoms that requires rescue therapy, exceptions related to prohibited medications, such as TCS use, will be permitted. The use of rescue therapy should be discouraged throughout the treatment phase of trial, and reserved for only severe symptoms associated with AD flares. In such cases, subjects may continue study participation, while continuing concomitant rescue therapy use; however, discontinuation of IP may be required depending on the type of rescue medication that is administered.

- Subjects requiring rescue therapy should consider the addition of TCS prior to considering systemic treatment. Any subject who requires TCS rescue therapy treatment are encouraged to continue the TCS for as brief a period as possible (eg less than 7 days), while continuing with treatment with IP, and maintaining the study visit schedule.
- Any subject requiring systemic rescue therapy to treat their AD during the treatment phase of the study will be discontinued from IP and will be encouraged to continue participation in the study without IP administration. Subjects who decline further participation in the study should proceed with the Early Termination Visit and follow up visit assessments. Subjects requiring systemic rescue therapy during the follow up period of the study should continue the study visits as planned. All instances of rescue therapy administration that occur during the course of study participation will be captured accordingly within the source documentation in the eCRF.

The impact of rescue therapy will also be evaluated by defining these endpoints as missing for subjects who initiate rescue therapy prior to Week 16 and analyzed according to methods described in Section 9.

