9.2. Study Population Definitions

The following analysis populations will be used in the statistical analysis:

Modified intent to treat (mITT) Population

All randomized participants who received at least 1 dose of IP.

The mITT population will be used as the primary population for all efficacy parameters. Subjects who prematurely withdraw from the trial for any reason and for whom an assessment is not performed for any reason will still be included in the mITT population. Subjects will be included in the treatment group to which they are randomized. Subjects who were randomized with a misreported stratum will be classified according to their original (misreported) stratum.

Safety Population

The Safety population will consist of all subjects who received at least one dose of IP. This population will be used for all summaries of safety data. Subjects randomized to placebo who receive any dose of CC-93538 will be summarized in the CC-93538 group. Subjects randomized to CC-93538 who receive only placebo will be summarized in the placebo group; otherwise, they will be summarized in the CC-93538 group.

Pharmacokinetic Population

All subjects who received at least one dose of active drug and have at least one measurable concentration data.

Biomarkers

All participants that received any study treatment and have any available biomarker measurement.

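### The main responder analyses credit clearance on systemic rescue to the assigned arm but count leaving as failure; counting systemic rescue as non-response is a cheap improvement

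*Combined protocol and SAP*

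**What the plan says.** - **Missing data, main analysis (Section 9.6.2.1).** For the two key secondary endpoints: "Missing endpoint values (eg, due to study dropout or other reasons for lack of assessment) will be imputed as non-responders". No other event is non-response in the main analysis.
- **Rescue (Section 9.6.2.1).** "A sensitivity analysis will be conducted based on defining subjects who initiate rescue therapy (prior to Week 16) as missing and treated as non-responders".
- **Other responder endpoints (Section 9.6.2.1).** EASI-90 and Pruritus NRS ≥4 follow the same rules: "The following endpoints will be analyzed in the same manner as the key secondary endpoints, excepting that p-values will not be provided".
- **IP after systemic rescue (Section 8.4).** "Any subject requiring systemic rescue therapy to treat their AD during the treatment phase of the study will be discontinued from IP". Section 7.2.6 repeats this and adds a second trigger: "Uses prohibited systemic immunosuppressive or immunomodulating drugs".
- **Staying in the study (Section 7.2.6).** "These subjects will be encouraged to remain in the study and complete all required study assessments". Sections 8.4 and 11.1 say the same, and Section 11.1 names efficacy evaluations.
- **Arm for analysis (Section 9.2).** "Subjects will be included in the treatment group to which they are randomized".

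**The concern.** Take two subjects in the same arm who both fail on IP and start a systemic drug. One stays, clears on that drug and attends Week 16; this subject is a responder for the randomized arm. The other leaves; this subject is a non-responder. What separates them is retention after failure and the effect of another drug, not the assigned regimen.

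The rule is therefore not a clean treatment-policy rule, because leaving already counts as failure. Nor does it isolate response to the assigned regimen, which is what a design that prohibits background AD therapy (Section 3.1) would lead one to expect. The plan names no estimand for these endpoints.

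This analysis supplies the p-values for the dose hierarchy on both key secondary endpoints. For EASI-90 and Pruritus NRS ≥4 only the estimates are affected. Small counts matter: at the planned placebo rate of 2%, one placebo responder is expected among 50 subjects.

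**Working it through.** **Inputs from the documents.** About 50 randomized per arm, 45 after 10% dropout; planned vIGA-AD response 2% on placebo and 25% on the QW dose, which is tested first; two-sided 0.05; stated power of more than 90% for at least one dose (Sections 9.3 and 9.6.2.1). Under fixed-sequence testing, power for at least one dose equals the power of the first test.

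**Step 1: the plan's own figure.** Pooled normal formula, with p̄ = (0.02 + 0.25)/2 = 0.135:

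power = Φ{[(p1 − p0)√n − 1.96√(2p̄(1 − p̄))] / √(p0(1 − p0) + p1(1 − p1))}

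- n = 45: (1.543 − 0.947)/0.455 = 1.31, power 0.905.
- n = 50: power 0.932.

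Both agree with the stated figure.

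**Step 2: exact baseline.** Missing values count as failures, so all treated subjects are analysed and n = 50 per arm is used. Stratum sizes are not given, so a single stratum is used. With x placebo and y active responders, m = x + y and N = 100, the CMH statistic is (y − m/2)² / [50²·m(N − m)/(N²(N − 1))]. Reject in favour of active if it exceeds 3.84 with y > x. Summing the two binomial probabilities over the rejection region gives 0.967 for 25% versus 2%. With 0, 1, 2 or 3 placebo responders, the active arm needs at least 4, 7, 8 or 10 to reject.

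**Step 3: the rule as written.** Rescue rates and response after rescue are assumptions; the documents give neither. Section 8.4 has TCS considered before systemic treatment, so low systemic-rescue rates are used. If 2% and 25% are the rates with rescue counted as failure, then

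rate as written = planned rate + (proportion rescued × 0.15).

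| Systemic rescue, placebo/active | Placebo | Active | Exact power |
|---|---|---|---|
| none | 2% | 25% | 0.967 |
| 5%/2% | 2 + 0.75 = 2.75% | 25 + 0.3 = 25.3% | 0.948 |
| 10%/5% | 2 + 1.5 = 3.5% | 25 + 0.75 = 25.75% | 0.927 |
| 5%/5% | 2.75% | 25.75% | 0.953 |
| 5%/10% | 2.75% | 25 + 1.5 = 26.5% | 0.961 |

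More rescue on placebo shrinks the difference: from 23 to 22.25 points in the 10%/5% case. More on active widens it: to 23.75 points in the 5%/10% case.

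Heavier assumptions do more. With 30% of rescued subjects responding, the pooled formula at n = 50 gives 0.850 for 10%/5% (5% versus 26.5%) and 0.747 for 20%/10% (8% versus 28%), against 0.932 without rescue.

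**Step 4: the other reading of the planning rates.** If 2% and 25% already describe the planned main analysis, which is the plain reading of Section 9.3, nothing is lost against plan. Counting systemic rescue as failure would then give 24.7% versus 1.25% (power 0.982) in the 5%/2% case and 24.25% versus 0.5% (0.993) in the 10%/5% case.

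**Step 5: a dose with no effect.** With 2% response in both arms and no rescue, the probability of rejecting in favour of active is 0.0065. With equal rescue and 15% of rescued subjects responding, it is 0.012 at 5%/5% (2.75% in both arms) and 0.017 at 10%/10% (3.5% in both). Both are below the one-sided 0.025.

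No EASI-75 planning rates are stated, so none were computed.

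**The case against.** The strongest defence is that this is a choice between two prespecified analyses. Counting rescue as non-response is already planned. Using observed data in the randomized arm is legitimate and matches the primary EASI analysis, where rescue is handled only in sensitivity analyses (Section 9.6.1.1). Section 9.1 leaves further detail to the SAP. All of this stands, and it is why the point is an improvement. It does not answer the mixed handling of those who stay and those who leave, or the question of which rule should supply the p-values.

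A reader might infer more than the documents support:

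- **That Section 8.4 already makes rescue non-response.** Its closing sentence describes an additional evaluation and refers to Section 9, which places it in the sensitivity analysis.
- **That false positives are inflated.** Rejection probabilities of 0.025 or 0.052 arise for a dose with no effect if rescue is 5% on placebo and 10% on active, or if true rates are 2% and 4%. Those cases describe a dose with more rescue or more response than placebo. Under randomization, a dose with no effect has equal expected rescue, as in Step 5.
- **That the power claim fails.** Holding active at 25% and raising placebo to 4% or 6% gives 0.890 or 0.775. At 15% response after rescue, this needs about 13% (0.02/0.15) or 27% (0.04/0.15) systemic rescue on placebo and none on active. The heavier cases in Step 3 also fall below 90%, but no rate in the documents supports them.

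**Conclusion.** The concern holds as a cheap improvement, not an error. As written, a subject who clears on systemic rescue after stopping IP is a main-analysis responder for the randomized arm, and one who leaves is not. This makes the dose comparison harder to interpret, with a bias whose direction depends on rescue by arm.

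The likely size is modest. Under the low assumed rescue rates (5%/2% or 10%/5%, 15% responding), power falls from 0.967 to 0.948 or 0.927, so the claim of more than 90% still holds. If the planning rates already describe the planned analysis, there is no loss against plan. No type I error problem is shown.

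The figures rest on assumed rescue and response rates, 50 subjects per arm and a single stratum. The reading that a subject who leaves is a non-responder also assumes that an Early Termination assessment is not used as the Week 16 value; the text does not provide for that.

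**What to change.** In Section 9.6.2.1 and the SAP, for vIGA-AD 0/1, EASI-75, EASI-90 and Pruritus NRS ≥4, write before unblinding:

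> Main analysis: subjects with a missing Week 16 value, and subjects who before Week 16 start systemic therapy for AD (systemic rescue or a prohibited systemic immunosuppressive or immunomodulating drug given for AD), whether before or after stopping IP and whatever the reason IP was stopped, are non-responders. Sensitivity analyses: (1) any rescue before Week 16, topical included, is also non-response (as now planned); (2) as observed regardless of rescue, with missing values as non-response (the current main rule). The number of such subjects will be reported by arm.

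The wording covers a subject who stops IP for another reason and then starts a systemic AD drug. It leaves out systemic drugs given for other conditions.

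**Cost.** Text changes and one more analysis run; no change to sample size or visits. Section 8.4 already captures rescue in the eCRF, and Section 8 requires all concomitant treatments "until the Final Safety Follow-up Visit, or Final Study Visit must be reported on the eCRF". The team should confirm that the indication is recorded, since the rule needs it.

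**Downsides to state in the plan.** The primary EASI analysis uses these subjects' observed scores, so it and EASI-75 will treat them differently. Topical rescue stays as observed in the main analysis; sensitivity analysis (1) shows its effect.

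The rules on rescue and on stopping IP are unchanged.
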